^c Includes FVIII activity level (chromogenic substrate FVIII assay and one-stage clotting FVIII assay), chromogenic Nijmegen-Bethesda Assay for hFVIII inhibitor level, and coagulation exploratory assay. Chromogenic Nijmegen-Bethesda Assay for hFVIII inhibitor level will be tested as deemed necessary by the Sponsor. If a subject has used FVIII within 72 hours of a measurement day, all efforts should be made to obtain FVIII activity measurements when a 72-hour interval without FVIII use is achieved; the 72-hour wash-out period is only intended for subjects who have achieved FVIII ≥ 5 IU/dL at 16 weeks after BMN 270 infusion and who have not resumed FVIII replacement therapy. If FVIII levels are elevated or stable over the course of several weeks, assessment of FVIII activity may be adjusted based on discussion between the Medical Monitor and the Investigator. A D-dimer may be considered under circumstances in which FVIII activity levels are above the normal physiological range and/or if there is a concern for a venous thromboembolism.

^d Collection for each matrix to occur until at least 3 consecutive results below the limit of detection are obtained; longer collection and testing may be performed based on batch testing schedules, result turnaround times, or discussions between Medical Monitor and Investigator. Collection and testing of semen samples must continue at least through Week 12, even if 3 consecutive results below the limit of detection in that compartment have already been recorded.

^e Blood samples will be collected to evaluate biochemical, molecular, cellular, and genetic/genomic aspects relevant to hemophilia A, coagulation, and/or AAV gene transfer, and to develop assays used for these evaluations. Subjects may choose to opt out of the exploratory genetic/genomic research being done to study or try to discover genes that are not yet known to be associated with hemophilia A. While exploratory samples will be collected at the time points indicated above, testing of these samples (including those for any other exploratory assessments) will be performed only as deemed necessary by the Sponsor.

^f Visits between scheduled clinic visits may be performed by a mobile nursing (MN) professional at the subject's home or another suitable location (if the subject has given written informed consent to participate in MN visits), or at the site or approved lab facility as a shortened lab draw-only visit. The MN service or site will collect blood samples at these visits. For site lab draw-only visits, sites will contact the subject via phone call or e-mail to collect information regarding adverse events, changes to concomitant medications, bleeding episodes, and FVIII use. For MN visits, the service will collect this information. Unscheduled visits may also be conducted by MN as appropriate.

^g Testing for reactivation of hepatitis B and hepatitis C only for subjects with a past medical history of hepatitis B or hepatitis C prior to study entry.

Table 9.1.3: Schedule of Events – Post-Infusion Follow-Up (Weeks 21-52)

Assessment	Follow-Up After BMN 270 Infusion-Weeks															
	21 ^f	22	23 ^f	24	25 ^f	26	28	30 ^f	32	34 ^f	36	40	44	48	50 ^f	52
Study Day*	148	155	162	169	176	183	197	211	225	239	253	281	309	337	351	365
Physical examination ^a		X		X		X	X		X		X	X	X	X		X
Weight						X			X		X		X			X
Assessment of Adverse Events and Concomitant Medications (including review of subject diary for bleeding and FVIII use)	X	X	X	X	X	X	X	X	X	X	X	X	X	X	X	X
Vital Signs				X		X			X		X	X	X	X		X
Blood chemistry, hematology, and coagulation tests ^b						X			X		X		X			X
Urine Tests ^b						X					X					X
Liver Tests ^b	X	X	X	X	X	X	X	X	X	X	X	X	X	X	X	X
hFVIII assays ^c	X	X	X	X	X	X	X	X	X	X	X	X	X	X	X	X
hFVIII protein assay				X		X			X		X	X	X	X		X
PCR of vector DNA in blood, saliva, urine, semen, and stools ^d						X			X		X		X			X
Immunogenicity AAV5 TAb Assay						X					X					X
AAV5 TI Assay						X					X					X
hFVIII TAb				X		X					X					X
IFNg ELISpot		X		X		X					X					X
Plasma, PBMC, and RBC collection for exploratory biomarkers ^e		X				X	X				X		X			X
Complement Panel and Exploratory Cytokine Profiling ^b				X		X					X					X
Serum for exploratory biomarkers ^e				X		X					X					X
Exploratory CK18 assessment	X	X	X	X	X	X	X	X	X	X	X	X	X	X	X	X

Assessment	Follow-Up After BMN 270 Infusion-Weeks															
	21 ^f	22	23 ^f	24	25 ^f	26	28	30 ^f	32	34 ^f	36	40	44	48	50 ^f	52
Study Day*	148	155	162	169	176	183	197	211	225	239	253	281	309	337	351	365
Haemo-QOL-A assessment						X										X
EQ-5D-5L						X										X
WPAI+CIQ:HS						X										X
PROBE						X										X
Testing for reactivation of hepatitis B and hepatitis C										X ^g						
Optional liver biopsy ^h						X										X
Liver ultrasound ⁱ																X

* Visit windows are \pm 48 hours.

^a Brief physical examination should be done at all visits where a physical examination is indicated except Week 26 and Week 52, where a complete physical examination should be performed. Additional physical exams may be done at the discretion of the PI.

^b Refer to [Table 9.7.8.2.1](#) for laboratory assessments to be included and for complement panel tests, and to [Table 9.7.8.4.1](#) for liver tests (LTs). LT assessment may be checked more frequently when ALT values are $>$ ULN or ≥ 1.5 times baseline value or based upon discussion between the Medical Monitor and the Investigator. Subjects with $>$ ULN or ≥ 1.5 times baseline value during the study and either an alternative etiology considered or for further evaluation of the lab abnormality may undergo additional evaluations (eg, imaging studies including MRI or ultrasound, additional blood tests, and/or liver biopsy) at the discretion of the Investigator. Additional testing of FVIII and LTs during any study week may be performed if: the ALT has increased to ≥ 1.5 times baseline value or $>$ ULN or after a discussion between the Medical Monitor and the Investigator based on a review of subject data. If FVIII levels and/or ALT values are stable over the course of several weeks, assessment of FVIII activity and ALT levels may be adjusted based on discussion between the Medical Monitor and the Investigator. In case of a safety concern, additional unscheduled laboratory tests may be performed locally (at the Investigator's discretion) in order to facilitate timely and appropriate clinical management decisions; where possible, a matched sample for testing at the central laboratory should be collected (using the Unscheduled Visit lab kit) at the same time as the local unscheduled sample. While exploratory samples for cytokine profiling will be collected at the time points indicated above, testing of these samples will be performed only as deemed necessary by the Sponsor.

^c Includes FVIII activity level (chromogenic substrate FVIII assay and one-stage clotting FVIII assay), chromogenic Nijmegen-Bethesda Assay for hFVIII inhibitor level, and coagulation exploratory assay. Chromogenic Nijmegen-Bethesda Assay for hFVIII inhibitor level will be tested as deemed necessary by the Sponsor. If a subject has used FVIII within 72 hours of a measurement day, all efforts should be made to obtain FVIII activity measurements when a 72-hour interval without FVIII use is achieved; the 72-hour wash-out period is only intended for subjects who have achieved FVIII ≥ 5 IU/dL at 16 weeks after BMN 270 infusion and who have not resumed FVIII replacement therapy. If FVIII levels are elevated or stable over the course of several weeks, assessment of FVIII activity may be adjusted based on discussion between the Medical Monitor and the Investigator. A D-dimer may be considered under circumstances in which FVIII activity levels are above the normal physiological range and/or if there is a concern for a venous thromboembolism.

^d Collection for each matrix to occur until at least 3 consecutive results below the limit of detection are obtained; longer collection and testing may be performed based on batch testing schedules, result turnaround times, or discussions between Medical Monitor and Investigator.

^e Blood samples will be collected to evaluate biochemical, molecular, cellular, and genetic/genomic aspects relevant to hemophilia A, coagulation, and/or AAV gene transfer, and to develop assays used for these evaluations. Subjects may choose to opt out of the exploratory genetic/genomic research being done to study or try to discover genes that are not yet known to be associated with hemophilia A. While exploratory samples will be collected at the time points indicated above, testing of these samples (including those for any other exploratory assessments) will be performed only as deemed necessary by the Sponsor.

^f Visits between scheduled clinic visits may be performed by a mobile nursing (MN) professional at the subject's home or another suitable location (if the subject has given written informed consent to participate in MN visits), or at the site or approved lab facility as a shortened lab draw-only visit. The MN service or site will collect blood samples at these visits. For site lab draw-only visits, sites will contact the subject via phone call or e-mail to collect information regarding adverse events, changes to concomitant medications, bleeding episodes, and FVIII use. For MN visits, the service will collect this information. Unscheduled visits may also be conducted by MN as appropriate.

^g Testing for reactivation of hepatitis B and hepatitis C only for subjects with a past medical history of hepatitis B or hepatitis C prior to study entry.

^h Optional liver biopsy should be obtained within two weeks of Week 26. Additional follow-up liver biopsy will be obtained within two weeks of Week 52. Subjects should fast for at least 8 hours prior to liver ultrasound and optional liver biopsies.

ⁱ Additional liver ultrasounds may be performed prior to Week 52 at the discretion of the Investigator.

Table 9.1.4: Schedule of Events-Post-Infusion Follow-Up (Year 2-Year 5)

Assessment	Years 2-5*			End of Year Visit				ETV
	Years 2-5	Year 2	Year 3-5	Year 2	Year 3	Year 4	Year 5	
Study Week*	Q12W	Q4W ^g	Q6W ^g	W104	W156	W208	W260	
Physical examination ^b	X						X	X
Weight ^b	X ^a						X ^a	X
Assessment of Adverse Events and Concomitant Medications (including review of subject diary for bleeding and hemophilia therapy use)	X	X	X				X	X
Vital Signs	X						X	X
Blood chemistry, hematology, and coagulation tests ^c	X ^a						X ^c	X
Urine Tests ^c	X ^a						X ^c	X
Liver Tests ^c	X	X	X				X	X
hFVIII assays ^d	X	X	X				X	X
hFVIII protein assay	X						X	X
PCR of vector DNA in blood, saliva, urine, and stools	(X) ^e						(X) ^e	(X) ^e
PCR of vector DNA in semen	(X) ^e	(X) ^e	(X) ^e				(X) ^e	(X) ^e
Immunogenicity AAV5 TAb Assay							X	X
AAV5 TI Assay							X ^j	X ^j
hFVIII TAb	X						X	X
IFNg ELISpot ^a	X ^a						X	X
Plasma, PBMC, and RBC collection for exploratory biomarkers ^f	X						X	X
Serum for exploratory biomarkers ^f	X						X	X
Exploratory CK18 assessment	X	X	X				X	X
Haemo-QoL-A assessment	X ^a						X ^a	X
EQ-5D-5L	X ^a						X ^a	X

Assessment	Years 2-5*			End of Year Visit				ETV
	Years 2-5	Year 2	Year 3-5	Year 2	Year 3	Year 4	Year 5	
Study Week*	Q12W	Q4W ^g	Q6W ^g	W104	W156	W208	W260	
WPAI+CIQ:HS	X ^a				X ^a			X
PROBE	X ^a				X ^a			X
Optional liver biopsy ^h					X			
Liver ultrasound ⁱ					X			

* Visit windows are \pm 2 weeks for visits in Years 2-5.

^a These assessments need to be performed only at every other Q12W and every End of Year visit (ie, Weeks 76, 104, 128, 156, 180, 208, 232, and 260).

^b Complete physical examination should be performed at the End of Year visits (genitourinary examination may be deferred); brief physical exam may be performed at other study visits. Weight should be recorded at the second Q12W visit each year and at every End of Year visit during Years 2-5.

^c Refer to [Table 9.7.8.2.1](#) for laboratory assessments to be included, and to [Table 9.7.8.4.1](#) for liver tests. LT assessment may be checked more frequently when ALT values are $>$ ULN or \geq 1.5x baseline value or based upon discussion between the Medical Monitor and the Investigator. Subjects with ALT $>$ ULN or \geq 1.5x baseline value during the study and either an alternative etiology considered or for further evaluation of the lab abnormality may undergo additional evaluations (eg, imaging studies including MRI or ultrasound, additional blood tests, and/or liver biopsy) at the discretion of the Investigator. Additional testing of FVIII and LTs during any study week may be performed if: the ALT has increased to \geq 1.5x baseline value or $>$ ULN or after a discussion between the Medical Monitor and the Investigator based on a review of subject data. If FVIII levels and/or ALT values are stable over the course of several weeks, assessment of FVIII activity and ALT levels may be adjusted based on discussion between the Medical Monitor and the Investigator. During Years 2-5 of the Post-Infusion Follow-Up period, urine tests and blood, chemistry, and coagulation tests should be performed at the second Q12W visit each year and at every End of Year visit. In case of a safety concern, additional unscheduled laboratory tests may be performed locally (at the Investigator's discretion) in order to facilitate timely and appropriate clinical management decisions; where possible, a matched sample for testing at the central laboratory should be collected (using the Unscheduled Visit lab kit) at the same time as the local unscheduled sample

^d Includes FVIII activity level (chromogenic substrate FVIII assay and one-stage clotting FVIII assay), chromogenic Nijmegen-Bethesda Assay for hFVIII inhibitor level, coagulation exploratory assay. Chromogenic Nijmegen-Bethesda Assay for hFVIII inhibitor level will be tested as deemed necessary by the Sponsor. If a subject has used FVIII within 72 hours of a measurement day, all efforts should be made to obtain FVIII activity measurements when a 72-hour interval without FVIII use is achieved; the 72-hour wash-out period is only intended for subjects who have achieved FVIII \geq 5 IU/dL at 16 weeks after BMN 270 infusion and who have not resumed FVIII replacement therapy. If FVIII levels are elevated or stable over the course of several weeks, assessment of FVIII activity may be adjusted based on discussion between the Medical Monitor and the Investigator. A D-dimer may be considered under circumstances in which FVIII activity levels are above the normal physiological range and/or if there is a concern for a venous thromboembolism. If a subject tests positive in the Bethesda assay (with Nijmegen modification) during Years 3-5, a fresh sample should be collected within 4 weeks of the initial visit that had a positive result.

^e Sample testing during Years 2-5 is not required if at least 3 consecutive samples were below the limit of detection during Year 1; additional collection and testing may be performed based on batch testing schedules, result turnaround times, or discussions between Medical Monitor and Investigator. Subjects who have not had 3 consecutive semen samples below the limit of detection by Week 52 should continue to have PCR testing of semen every 4 weeks (during Year 2) or every 6 weeks (during Years 3-5) until 3 consecutive samples below the limit of detection are documented (or upon consultation between the Investigator and Medical Monitor).

^f Blood samples will be collected to evaluate biochemical, molecular, cellular, immunological, and genetic/genomic aspects relevant to hemophilia A, coagulation, and/or AAV gene transfer, and to develop assays used for these evaluations. Subjects may choose to opt out of the exploratory genetic/genomic research being done to study or try to discover genes that are not yet known to be associated with hemophilia A. While exploratory samples will be collected at the time points indicated above, testing of these samples will be performed only as deemed necessary by the Sponsor.

^g Subjects who meet the definition of treatment failure to BMN 270 therapy after Week 52 may omit the Q4W and Q6W visits during Years 2-5, and must attend only the Q12W and End of Year visits. Subjects who are not attending the Q4W/Q6W visits during Years 2-5 may receive a scheduled monthly follow-up telephone call from the site to ask about adverse events, concomitant medications, and bleeding events/FVIII replacement usage. Such subjects following the abbreviated schedule who have not yet cleared vector shedding in semen must still provide samples Q4W (during Year 2) or Q6W (during Years 3-5) until vector shedding has been cleared, either by reporting to the site to provide samples or by providing those samples to a MN professional. Unscheduled visits may also be conducted by MN as appropriate.

^h An optional liver biopsy may be performed at any time between Years 2-5 of the study. The optional biopsy would be triggered by a FVIII activity decline by > 50% from steady-state, over 2 consecutive measurements, or by a sustained ALT rise > ULN. If neither trigger is observed, the optional biopsy should be performed at the end of Year 5.

ⁱ Additional liver ultrasounds may be performed at interim timepoints (ie, between the End of Year visits) at the discretion of the Investigator.

^j AAV5 TI Assay should be performed only at the end of the study (either the Year 5 End of Year Visit, or at the ETV for subjects who withdraw prior to the end of Year 5).

Table 9.1.5: Schedule of Events-Optional Liver Biopsy

	Within 28 Days Before Biopsy Day	Within 7 Days Before Biopsy Day	Biopsy Day (BD)
Informed Consent for Liver Biopsy Procedure	X		
Liver Ultrasound ^a	X		
Physical examination	X		X
Hematology, Coagulation, Chemistry Assessments ^b	X		X
Liver Tests ^b	X		X
FibroScan	X		
FVIII Activity Level Assessment (central and local)		X	X*
Exploratory CK18 and Grp78 assessment		X	X*
Pre-Biopsy Consultation ^c		X	
Liver Biopsy ^d			X
PBMC Collection (whole blood draw)			X ^e

* If the Day -7 and biopsy day visits occur on the same day, these tests do not need to be duplicated.

^a Liver ultrasound must be performed within 28 days prior to the scheduled biopsy. Subjects should fast for at least 8 hours prior to liver ultrasound.

^b Refer to [Table 9.7.8.2.1](#) for laboratory assessments to be included, and to [Table 9.7.8.4.1](#) for liver tests.

^c Subjects will undergo a pre-biopsy consultation with the Investigator (treating hematologist) and hepatologist and/or radiologist.

^d Subjects should fast for at least 8 hours prior to optional liver biopsy. Biopsy will be a percutaneous or transjugular biopsy under ultrasound guidance, performed according to the standard procedure of the institution. If only a small amount of tissue (< 2 cm) is obtained at the time of the biopsy, the subject may be asked to consent for a second pass. In this case, the original < 2 cm sample should still be retained and handled according to the instructions for handling biopsy specimens in the Laboratory Manual. Following completion of the biopsy, the subject should remain in the hospital under observation for at least 4-6 hours. Overnight post-procedure observation may be done at the Investigator's discretion.

^e Blood draw for PBMC collection should be performed on the biopsy day or ± 1 week from the biopsy day.

Table 9.1.6: Suggested Schedule of Events-Prophylactic Corticosteroids

Assessment	D1	Corticosteroid Treatment Period ^b																			Post-Corticosteroid Period ^c				
		Week																			Week				
		1	2	3	4	5	6	7	8	9	10	11	12	13	14	15	16	17	18	19	20	21	22	23	32
Prophylactic corticosteroid dose (mg/day)	40 mg	40 mg	40 mg	40 mg	40 mg	40 mg	40 mg	40 mg	40 mg	35 mg	35 mg	30 mg	30 mg	25 mg	25 mg	20 mg	20 mg	15 mg	10 mg	5 mg					
FVIII activity testing	X	X	X	X	X	X	X	X	X	X	X	X	X	X	X	X	X	X	X	X	X	X	X	X	
Liver tests	X	X	X	X	X	X	X	X	X	X	X	X	X	X	X	X	X	X	X	X	X	X	X	X	
Hepatitis B testing ^d							X													X					X
HCV Viral Load ^d							X													X					X

^a This table provides an example of a prophylactic corticosteroid course. Clinical judgment, weighing the potential risks and benefits of corticosteroid treatment, should always be exercised when considering adjustment of corticosteroid doses, and discussions between the Investigator and Medical Monitor are advised for any questions or concerns. Dosages are for prednisone or an equivalent dose of another corticosteroid. FVIII and liver tests are also reflected in the Schedule of Events for the study.

^b Following initiation or completion of corticosteroid regimen, if a recurrence of ALT values > ULN or $\geq 1.5 \times$ baseline value is reported, corticosteroid management decisions will be based on discussions between the Investigator and Medical Monitor. Modification of the corticosteroid regimen may take into consideration timing of ALT elevation (prior to or after Week 52), as well as possible confounders for the ALT elevation and adverse events related to corticosteroid dosing. Guidance for tapering oral corticosteroid dosing can be found in Section 9.4.8.2, although a discussion between the PI and Medical Monitor should take place prior to tapering the corticosteroid dose.

^c After discontinuation of oral corticosteroids, weekly labs for ALT levels and FVIII activity will be measured once a week for 4 weeks to ensure stability in values.

^d Should only be performed in subjects with a history of hepatitis B or hepatitis C prior to study entry. Tests are also reflected in the Schedule of Events for the study.

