9.3.2 Exclusion Criteria

Individuals who meet any of the following exclusion criteria will not be eligible to participate in the study:

1. Subjects with detectable pre-existing antibodies to the AAV5 capsid are excluded with the following exception: up to 25% of subjects may have detectable pre-existing AAV5 capsid antibodies with titer level below the minimum required dilution (< 20).
2. Any evidence of active infection, including COVID-19, or any immunosuppressive disorder, except for HIV infection. HIV-positive patients who meet all other eligibility criteria may be included if they have a CD4 count > 200/mm³ and an undetectable viral load (unquantifiable viral load as defined as less than the limit of quantification by the testing laboratory's assay is permitted) while receiving an antiretroviral therapy (ART) regimen that does not contain efavirenz or another potentially hepatotoxic ART.
3. Significant liver dysfunction with any of the following abnormal laboratory results:
 - ALT (alanine aminotransferase) > 1.25x ULN;
 - AST (aspartate aminotransferase) > 1.25x ULN;
 - GGT (gamma-glutamyltransferase) > 1.25x ULN;
 - Total bilirubin > 1.25x ULN;
 - Alkaline phosphatase > 1.25x ULN; or

- INR (international normalized ratio) ≥ 1.4 .

Subjects whose liver laboratory assessments fall outside of these ranges may undergo repeat testing of the entire liver test panel within the same Screening window and, if eligibility criteria are met on retest, may be enrolled after confirmation by the Medical Monitor.

4. FibroScan or prior liver biopsy showing significant fibrosis of 3 or 4 as rated on a scale of 0-4 on the Batts-Ludwig ([Batts 1995](#)) or METAVIR ([Bedossa 1996](#)) scoring systems, or an equivalent grade of fibrosis if an alternative scale is used.
5. Evidence of any bleeding disorder not related to hemophilia A.
6. Platelet count of $< 100 \times 10^9/L$.
7. Creatinine $\geq 1.5 \text{ mg/dL}$.
8. Liver cirrhosis or other clinically significant liver disease of any etiology as assessed by FibroScan or liver ultrasound.
9. Chronic or active hepatitis B as evidenced by positive serology testing (hepatitis B surface antigen [HBsAg], hepatitis B surface antibody [HBsAb], and hepatitis B core antibody [HBcAb]) and confirmatory HBV DNA testing. Refer to the Centers for Disease Control (CDC) table for the interpretation of serological test results in the Laboratory Manual.

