Recurrent ALT elevations	If the subject has recurrent ALT elevations (\geq 1.5x Baseline or $>$ ULN) and there are no safety concerns, the decision regarding management may be made at the discretion of the Investigator after discussion with the Medical Monitor

For any scenarios that are not accounted for in the above table, a discussion should take place between the Investigator and Medical Monitor regarding corticosteroid dose adjustments.

When ruling out alternative viral or autoimmune hepatitis as part of the elevated ALT workup, the following tests should be performed ([Table 9.4.8.2.2.2](#)):

Table 9.4.8.2.2.2: Viral and Autoimmune Hepatitis Testing

Viral Hepatitis Workup PCR Testing	Autoimmune Hepatitis Workup Testing
Hepatitis A	Smooth muscle antibody
Hepatitis B	Mitochondrial antibody
Hepatitis C	Liver/kidney microsomal antibodies
Hepatitis E	Antinuclear antibody (ANA) HEP-2
Cytomegalovirus (CMV)	
Epstein-Barr virus (EBV)	
Herpes simplex virus (HSV) 1 & 2	

After discontinuation of reactive oral corticosteroids, labs for ALT and FVIII levels will be measured once a week for 4 weeks to ensure stability in values.

Following completion of prophylactic oral corticosteroids, if increased ALT levels (eg, > ULN or ≥ 1.5 x baseline value) are reported, corticosteroid management decisions will be based on discussions between the Investigator and Medical Monitor. Modification of the corticosteroid regimen may take into consideration possible confounders for the ALT elevation and impact on FVIII expression.

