Management and monitoring of reactions to corticosteroids should be determined by the Investigator's clinical judgment in consultation with the Sponsor's Medical Monitor. This includes the contraindicated use of NSAIDs during corticosteroid treatment and specific monitoring not already covered by the SoA. The use of COX-2 inhibitors, while not contraindicated during corticosteroid treatment, should be limited, if possible. Practical management to prevent complications related to oral corticosteroid therapy may be undertaken at the discretion of the Investigator (eg, evaluation of glucose intolerance, hyperlipidemia). Alternative, non-steroidal systemic immunosuppressive agents may be used, following a discussion between the Investigator and the Medical Monitor, should corticosteroid use be deemed by an Investigator to be clinically ineffective, not tolerated, and/or contraindicated. Hepatitis B status and HCV viral load will be rechecked 6 weeks after the start of oral corticosteroid/immunosuppressive agent treatment and then 1 week and 13 weeks after the completion of oral corticosteroid/immunosuppressive agent treatment in subjects with a history of hepatitis B or hepatitis C. All adverse events (including any adverse events suspected to be caused by or related to corticosteroid/immunosuppressive agent use) should be reported as outlined in Section 10 of the protocol.

Subjects on corticosteroids should receive appropriate counseling and support regarding side effects from the Investigator or the treating institution (eg, listings of side effects and when to notify carers, wallet card for emergencies if on steroids, etc.). Additional management, including the co-prescription of additional medications to prevent complications related to corticosteroid therapy, may be undertaken at the discretion of the Investigator, including, but not limited to, prophylaxis against the occurrence of gastric ulcers, osteoporosis, and infections. The above guidance should also be followed in the event that an alternative immunosuppressive agent is used, as applicable.

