9.7.8.4 Liver and Hepatitis Testing

Subjects will be screened for evidence of previous or active hepatitis B or hepatitis C infection at Screening; hepatitis B screening should include HBsAg, HBsAb, and HBcAb. Subjects with documented results showing an absence of active hepatitis B or hepatitis C infection (as measured by negative surface antigen or DNA for hepatitis B or negative RNA testing for hepatitis C) 30 days prior to providing signed informed consent do not need to repeat those tests during the screening period.

Evidence of ongoing hepatitis B or hepatitis C infection is exclusionary. Subjects with a history of hepatitis B or hepatitis C infection prior to study entry will be tested for hepatitis B and hepatitis C reactivation at the timepoints listed in [Table 9.1.6](#). Subjects with a history of hepatitis B or hepatitis C will be asked for information about the treatments received as part of their medical history assessment at Screening.

A liver ultrasound, fasting FibroTest, and liver tests (LTs) during Screening will be performed to assess for clinically significant liver disease and HCC. A FibroScan may also

be performed during Screening at the discretion of the Investigator. Fasting FibroTest results must be available prior to BMN 270 infusion.

Where a biopsy has been taken for safety-related reasons or was available from a past procedure, the Sponsor may request the biopsy information to help evaluate the impact of BMN 270 on the liver. The Sponsor may request that slides from a liver biopsy be made available for additional histopathological review.

LTs will be monitored on a regular basis; at each time point, the following LTs should be assessed:

Table 9.7.8.4.1: Liver Tests

Liver Tests (LTs)			
Alkaline Phosphatase	AST (SGOT)	Total Bilirubin	LDH
ALT (SGPT)	Direct Bilirubin	GGT	

ALT, alanine aminotransferase; AST, aspartate aminotransferase; GGT, gamma-glutamyltransferase; LDH, lactate dehydrogenase; SGOT, serum glutamic-oxaloacetic transaminase; SGPT, serum glutamic-pyruvic transaminase

Elevated ALT levels (above the upper limit of normal range) should be evaluated according to the plan outlined in [Table 9.4.8.2.2.1](#) (note that these evaluations may indicate additional testing of LTs and FVIII levels at unscheduled visits; these unscheduled laboratory tests may be completed by a mobile nursing professional at sites where the use of MN services has been approved).

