10.4.1.4 Pre-existing Conditions

A pre-existing condition is one that is present prior to administration of BMN 270. Such conditions should be recorded as medical history on the appropriate eCRF.

A pre-existing condition should be recorded as an AE or SAE during the study **only** if the frequency, intensity, or character of the condition worsens during the study period. It is important to convey the concept that a pre-existing condition has changed by including applicable language in the verbatim description of the event (eg, *more frequent* headaches).

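### A man found HBcAb-positive and HBV-DNA-negative at Screening, with no known past hepatitis B, can be dosed, and the literal wording leaves him out of reactivation testing at Weeks 6, 20 and 32

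*Protocol*

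**What the plan says.** Section 9.7.8.4 states the purpose of the serology: "Subjects will be screened for evidence of previous or active hepatitis B or hepatitis C infection at Screening". The hepatitis B panel must include HBsAg, HBsAb and HBcAb.

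Exclusion criterion 9 (Section 9.3.2, repeated in the Synopsis) removes chronic or active hepatitis B. The evidence it asks for is positive serology (HBsAg, HBsAb, "and hepatitis B core antibody [HBcAb]) and confirmatory HBV DNA testing"). Section 9.7.8.4 adds that ongoing infection excludes.

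After dosing, footnote g of Tables 9.1.2 and 9.1.3 gives reactivation testing "only for subjects with a past medical history of hepatitis B or hepatitis C prior to study entry". Sections 12.5.13 (Weeks 6 and 20) and 12.6.4 (Week 32) repeat that restriction. Three further places use a slightly different term:

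- Table 9.1.6 footnote d: "Should only be performed in subjects with a history of hepatitis B or hepatitis C prior to study entry".
- Section 9.7.8.4: "Subjects with a history of hepatitis B or hepatitis C infection prior to study entry will be tested".
- Section 9.4.8.2.2 sets a check 6 weeks after corticosteroids or other immunosuppressants start, with two later ones: "1 week and 13 weeks after the completion of oral corticosteroid/immunosuppressive agent treatment in subjects with a history of hepatitis B or hepatitis C".

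**The concern.** The protocol looks for past hepatitis B by serology, but it selects subjects for follow-up testing by history. The two groups differ for a man who does not know that he was infected: his HBcAb is positive, his HBV DNA is negative, and nothing about hepatitis B appears in his record before Screening.

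Section 9.4.8.2.2 ties reactivation testing to immunosuppression. Every subject takes the 19-week prophylactic course, at 40 mg/day through Week 8 in the suggested schedule of Table 9.1.6. Some may add reactive corticosteroids from 60 mg/day, or tacrolimus or mycophenolate (Section 9.4.8.2.2). This man has the same exposure as a man with a recorded history, yet on a literal reading he receives none of the scheduled tests. Two sites could handle the same patient differently and both believe that they comply.

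**Working it through.** The check is mainly a comparison of text; the only arithmetic is the test schedule.

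**Can he be dosed?** Criterion 9 joins positive serology and confirmatory HBV DNA with *and*. A man who is HBcAb-positive but DNA-negative does not meet it. The ongoing-infection rule of Section 9.7.8.4 does not reach him either, provided that he is HBsAg-negative. Criterion 16 is discretionary and does not require his exclusion. So he can be dosed.

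**How many scheduled tests are at stake?** Inputs: a 19-week prophylactic course (Section 9.1), with checks 6 weeks after its start and 1 and 13 weeks after its end (Section 9.4.8.2.2).

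- 6 weeks after the start: Week 6
- 1 week after the end: 19 + 1 = Week 20
- 13 weeks after the end: 19 + 13 = Week 32

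This reproduces the weeks in Table 9.1.6 and in Sections 12.5.13 and 12.6.4. There are 3 scheduled tests.

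**Who gets them?**

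| Place | Wording of the trigger | Names HBcAb? |
|---|---|---|
| Table 9.1.2, footnote g | past medical history | no |
| Table 9.1.3, footnote g | past medical history | no |
| Section 12.5.13 | past medical history | no |
| Section 12.6.4 | past medical history | no |
| Table 9.1.6, footnote d | history | no |
| Section 9.4.8.2.2 | history | no |
| Section 9.7.8.4 | history of infection | no |

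Four places say past medical history and three say history: 4 + 3 = 7. None of the seven makes a positive HBcAb a way into the group.

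**Is serology treated as part of the history?** Section 12.2 lists the full medical history, including hepatitis B, as one Screening item and the hepatitis B screen as another. Subjects with a history are asked what treatment they received. A man unaware of his infection has nothing to report. The text therefore gives a site reasonable grounds to leave him out.

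**Result.** On the literal reading he has 0 of 3 scheduled tests; on the broad reading he has 3 of 3.

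**The case against.** The strongest reply is that the broad reading is the natural one. Section 9.7.8.4 screens for previous infection, and its next paragraph tests those with a history of infection before study entry. A positive HBcAb is evidence of such an infection, and the narrow reading leaves the screen for past infection with no stated use in a man with no known history. Screening comes before enrolment, which Section 12.3 dates to the Baseline visit. Section 10.4.1.4 says of conditions present before dosing: "Such conditions should be recorded as medical history on the appropriate eCRF". Table 9.1.6 states that its tests also appear in the Schedule of Events, which suggests that one group was meant throughout. This reading is fair, and for that reason the point is an ambiguity and not an instruction to omit testing. But the protocol never states it. Section 10.4.1.4 is a recording rule for adverse events and does not define who is tested.

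A second reply is that he is monitored anyway. Liver tests are weekly through Week 26 and continue at each visit to Week 52. An ALT above ULN or at least 1.5 times baseline prompts a repeat within 24 to 72 hours and a search for other causes. The hepatitis B PCR in that work-up carries no history restriction: "When ruling out alternative viral or autoimmune hepatitis as part of the elevated ALT workup, the following tests should be performed". This stands as a real fallback. It starts only after ALT has risen, however, and it applies equally to men with a known history, for whom the sponsor still scheduled three tests in advance. It does not replace those tests.

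Third, the Laboratory Manual and the corticosteroid prescription guidelines may say how to classify or follow a positive HBcAb, and the Medical Monitor approves each enrolment. Those two documents are not available here. Criterion 9 refers to the Laboratory Manual's table only for interpreting serology in the eligibility decision. Nor does the protocol itself say that such a man needs testing. The case for it rests on the protocol's own logic of testing men with past infection while they are immunosuppressed.

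**Conclusion.** The concern holds. A man who is HBsAg-negative, HBcAb-positive and HBV-DNA-negative, with no known hepatitis B, can be dosed. Under the wording used in four of the seven places, followed literally, he misses all three scheduled reactivation tests, which cover the 19-week course and the 13 weeks after it. The other three places can be read to include him, but none says so.

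The conclusion assumes that he is HBsAg-negative, that no one uses criterion 16 to exclude him, and that the site takes history to mean what was known before Screening. The documents do not give the number of affected subjects; in a study of about 20 it may be zero. The point concerns subject safety and consistency between sites. It does not touch the primary endpoint or the sample size. It should be corrected, and confidence is medium because the broad reading is arguable.

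**What to change.** Define the reactivation-testing group once as subjects with a history of hepatitis B or hepatitis C, or with a positive HBcAb at Screening. Use that phrase in footnote g of Tables 9.1.2 and 9.1.3, footnote d of Table 9.1.6, and Sections 9.4.8.2.2, 9.7.8.4, 12.5.13 and 12.6.4.

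Optionally, state in Section 9.7.8.4 that the 30-day waiver applies test by test, so that a recent negative surface antigen or DNA result does not stand in for HBcAb and every dosed subject has a core-antibody result. The present wording may already intend this.

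The cost is one phrase in seven places and the three already-planned tests for each subject added. Eligibility, endpoints and sample size do not change.
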